10.1 EVALUATION DURING TREATMENT/INTERVENTION

	Pre-Study ^f	Cycle 1 Week 1 ^t	Cycle 1 Week 3	Cycle 2+ Week 1 ^u	Off Study ^l
Durvalumab ^a		X		X	
Adherenceto low iodine diet			X ^h		
Thyrogen			X ⁱ		
100 mCi (+/- 10 mCi) ^{131}I (RAI)			X ^j		
Concurrent meds	X	X	X	X	X
Physicalexam	X	X ^g	X	X	X
Vital signs (pulse, blood pressure)	X	X ^g	X	X	X
Weight	X	X ^g	X	X	X
Performance status	X	X ^g	X	X	X
EKG ^s	X		X		
Hematology tests ^b	X	X ^g	X ⁱ	X	X
Clinical chemistry tests ^b	X	X ^g	X ⁱ	X	X
Urinalysis ^b	X	X ^g		X	
TSH, TG, and antibody serologies for TG, TPO, TSHR ^r		X	X ^f	X	X
Beta-HCG (serum or urine)	X ^c		X ^k		
Research peripheral blood collection ^o			X	X ^p	X ^p
DLT Monitoring ^d		X		- X	
Adverse event evaluation		X-			X (Monitored for 90 days following the last dose of durvalumab.)
Radiologic evaluation (CT(s) and/or MRI(s)) for tumor measurements ^e NO IODINATED CONTRAST IS ALLOWED PRIOR TO RAI ADMINISTRATION	X		CT and/or MRI will be performed every 8 weeks (+/- 1 week) (or approximately every 2 cycles). After 6 months, scans will be performed every 12 weeks (+/- 1 week) (or approximately every 3 cycles). Objective responses should be confirmed with a second assessment performed at least 4 weeks later. Iodinated contrast may be used after RAI has been administered.		
Research blood draw ^m	X				
Research tumor biopsy ⁿ	X			X ⁿ	
Archival tissue collection ^q	X				

a: 1500 mg IV durvalumab will be administered during week 1 of every cycle. Dose adjustment is required for patients weighing <30 kg as detailed in Appendix 2. Patients will remain on durvalumab treatment until there is confirmed progression of disease, unacceptable toxicity, withdrawal of consent, or if the study physician feels removal from the study is in the patient's best interest. One exception to these discontinuation rules: given the potential for delayed responses following short periods of disease progression with immunotherapy, subjects may continue to receive therapy beyond radiographic progression if the investigator concludes that the subject is tolerating study drug and continued therapy may provide clinical benefit. If a dose of durvalumab is missed or held for unforeseen scheduling conflicts (e.g. extreme weather related issues, etc...), medical issues unrelated to study drug toxicities, or patient's personal conflicts (e.g. personal travel, holidays, etc...), durvalumab may be restarted at the investigator's discretion. The week that durvalumab dose is restarted will be considered Week 1; subsequent treatments/evaluations may then be scheduled accordingly.
 b: For components of the hematology tests, see Table 1 below. For components of the clinical chemistry test, see Table 2 below. For components of the urinalysis, see Table 3 below.
 c: Serum or urine Beta-hcg (for women of childbearing potential): for pre-study evaluation, this should be obtained within 7 days of starting the study.
 d: The DLT monitoring period will be 6 weeks beginning from the first durvalumab dose.
 e: The treating physician may reschedule radiology scans due to treatment delays at his or her discretion. If the patient has CT and/or MRI scans completed early for any reason (i.e. suspicion of disease progression), the next set of scans may be ordered in 8 weeks (+/- 1 week) from that assessment (or in 12 weeks (+/- 1 week) for patients who are on treatment for more than 6 months).
 f: All Pre-Study evaluations must be done within 4 weeks prior to the start of durvalumab unless otherwise specified.

- g: These Week 1 evaluations may be performed up to 7 days prior to starting treatment. It is unnecessary to repeat these laboratory tests if the screening assessments of the same tests were performed within 7 days prior to the first dose of therapy.
- h: Patients should start a low iodine diet for 5 days prior to the first Thyrogen injection, and maintain the diet through 1 day after RAI is given.
- i: 0.9 mg Thyrogen will be administered intramuscularly in 2 consecutive calendar days. RAI is administered the calendar day after the second Thyrogen injection. Performance of a post-RAI whole body scan will be done as per standard of care per investigator discretion. The administration of these agents and evaluations will be performed in clinic. **If modification of durvalumab dose is required prior to RAI therapy, a delay in the schedule of Thyrogen and RAI administration is allowed as long as it is given prior to the second durvalumab dose.**
- j: These laboratory tests preferably will be performed prior to the first Thyrogen injection (not required).
- k: Serum or urine beta-hcg (for women of childbearing potential) is to be completed within 2 days prior to administration of RAI.
- l: Off-study evaluation will be performed within 30 days of the patient's last dose of durvalumab.
- m: The research blood sample can be obtained any time (for germline DNA).
- n: Radiologic guidance (CT, MRI or ultrasound guided) approaches and obtaining multiple cores to ensure sufficient biopsy material (at least 3 cores preferred) are allowed as long as it is considered safe for the patient (image-guided biopsies will be performed by a radiology physician with the appropriate expertise). The first research biopsy will be performed any time prior to Week 1 Day 1; the second research biopsy will preferably be conducted during Cycle 2, Week 3 or 4 (though alternate timing during Cycle 2 or later is allowed per investigator discretion or for safety reasons related to RAI administration).
- o: Peripheral blood samples will be collected for peripheral T cell analysis as well as cfDNA analysis. For peripheral T cells, blood will be collected in 4 CPT tubes (BD, 8-ml capacity, total blood volume collected~32 ml for PBMC purification for flow cytometric analysis) and 1 PAXgene tube (BD order #762165 or equivalent) (for purification of RNA/DNA for TCR analysis). For cfDNA analysis, blood will be collected in 10-ml Cell-Free DNA BCT tubes (STRECK). These blood samples (peripheral T cells and cfDNA) will be collected Cycle 1/Week 1 (prior to durvalumab). In Cycle 1/Week 3 or 4, only the cfDNA sample will be drawn at various time points: on the day of first Thyrogen injection (but prior to Thyrogen injection) and on the day of RAI administration (but prior to RAI ingestion).
- p: Research blood collection (for peripheral T cell analysis and cfDNA analysis) after Cycle 1 will be conducted on Week 1 of Cycles 2, 3, and 4 (preferably prior to durvalumab administration, if possible), as well as Off Study. Cycle 2 cfDNA collection does not have to be performed if the Principle Investigator decides that it is redundant given the cfDNA collections performed for **footnote o**.
- q: Confirm availability of archival tumor tissue (if tissue is not already available at MSK, physical receipt of tissue is not required for study enrollment or initiation).
- r: TSH, thyroglobulin (TG), and antibody serologies for TG, thyroperoxidase (TPO), and TSH receptor (TSHR) will be drawn Cycle 1/Week 1 (prior to durvalumab). In Cycle 1/Week 3, TSH and TG will be drawn at various time points: on the day of first Thyrogen injection (but prior to Thyrogen injection) and on the day of RAI administration (but prior to RAI ingestion). Subsequently, TSH and TG will be drawn on Week 1 of every cycle. Additionally, antibody serologies for TG, TPO, TSHR will be required to be drawn on Week 1 of every even numbered cycle, up to and including Cycle 6.
- s: EKG will be performed in triplicate. Repeat the EKG in Cycle 1 (Week 3)(only 1 EKG required at that time point).
- t: If Cycle 1 Week 1 labs fall below screening requirements, the patient can start treatment at the discretion of the treating investigator if safety is not compromised.
- u: Week 1 evaluations/tests and research collections during Cycles 2 and beyond may be performed up to 3 days prior to the patient being treated.

NOTE: Timing/scheduling of the administration of Thyrogen, RAI, and subsequent durvalumab doses beyond the first one, as well as the requisite evaluations listed in the calendar, may be rescheduled at different days due to delays related to durvalumab toxicity, holiday schedules, patients' personal commitments or conflicts.

Table 1. Hematology Laboratory Tests

Basophils	Mean corpuscular volume
Eosinophils	Monocytes
Hematocrit	Neutrophils
Hemoglobin	Platelet count
Lymphocytes	Red blood cell count
Mean corpuscular hemoglobin	Total white cell count
Mean corpuscular hemoglobin concentration	

Table 2. Clinical chemistry (Serum or Plasma) Laboratory Tests

Albumin	Glucose
Alkaline phosphatase	
Alanine aminotransferase	Lipase
Amylase	Magnesium
Aspartate aminotransferase	Potassium
Bicarbonate	Sodium
Calcium	Total bilirubin ^a
Chloride	Total protein
Creatinine	Urea or blood urea nitrogen, depending on local practice

^a If Total bilirubin is $\geq 2 \times \text{ULN}$ (and no evidence of Gilbert's syndrome) then fractionate into direct and indirect bilirubin.

Table 3. Urinalysis Tests^a

Bilirubin	pH
Blood	Protein
Glucose	Specific gravity
Ketones	Colour and appearance

^a Microscopy should be used as appropriate to investigate white blood cells and use the high power field for red blood cells.

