11.1 TOXICITIES/SIDE EFFECTS

For adverse events (AEs) that are considered related to administration of durvalumab, the following may be applied:

- Following the first dose of durvalumab, subsequent administration of durvalumab can be modified based on toxicities observed (see **Appendix 1**). Dose reductions are not permitted.
- Treat each of the toxicities with maximum supportive care (including holding the agent suspected of causing the toxicity where required).
- If the symptoms promptly resolve with supportive care, consideration should be given to continuing the same dose of durvalumab along with appropriate continuing supportive care according to guidelines outlined in **Appendix 1**.
- If modification of durvalumab treatment is required prior to the administration of RAI, delay in giving Thyrogen and RAI therapy prior to the second dose of durvalumab is allowed if the patient remains on study.
- In addition, there are certain circumstances in which durvalumab should be permanently discontinued.
- Cycle 2 and 3 doses of durvalumab will not be held for hematologic cytopenias (leukopenia, anemia, neutropenia, thrombocytopenia), which can occur following RAI therapy.
- Re-starting of durvalumab administration after holding therapy for toxicity can be done at the investigator's discretion as long as criteria in **Appendix 1** are fulfilled. The week that durvalumab is re-started will then be considered to be Week 1. Subsequent treatments and evaluations can then be scheduled accordingly.

Based on the mechanism of action of durvalumab leading to T-cell activation and proliferation, there is the possibility of observing immune related Adverse Events (irAEs) during the conduct of this study. Potential irAEs include immune-mediated enterocolitis, dermatitis, hepatitis, and endocrinopathies. Subjects should be monitored for signs and symptoms of irAEs. In the absence of an alternate etiology (e.g., infection or PD) signs or symptoms of enterocolitis, dermatitis, hepatitis, and endocrinopathy should be considered to be immune-related.

Dose modification recommendations and toxicity management guidelines for immune-mediated reactions, for infusion-related reactions, and for non-immune-mediated reactions related to durvalumab are detailed in Appendix 1. In addition, management guidelines for adverse events of special interest (AESIs) are detailed in **Appendix 1**. All toxicities will be graded according to NCI CTCAE v4.0.

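### Tumour scans may move with dose delays, without a limit, so the dating of progression for PFS can depend on toxicity

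*Combined protocol and SAP*

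**What the plan says.** The schedule in Section 10.1 gives each imaging interval twice, once in weeks and once in cycles. For the first 6 months: "CT and/or MRI will be performed every 8 weeks (+/- 1 week) (or approximately every 2 cycles". Thereafter: "After 6 months, scans will be performed every 12 weeks (+/- 1 week) (or approximately every 3 cycles".

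Four clauses let evaluations follow dosing:

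- **Section 10.1, footnote e**, on scans specifically: "The treating physician may reschedule radiology scans due to treatment delays at his or her discretion".
- **Section 10.1, NOTE below the footnotes.** The evaluations listed in the calendar, of which radiology is one row, "may be rescheduled at different days due to delays related to durvalumab toxicity, holiday schedules, patients' personal commitments or conflicts".
- **Section 11.1.** After a toxicity hold the restart week becomes Week 1. "Subsequent treatments and evaluations can then be scheduled accordingly".
- **Section 10.1, footnote a**, for doses missed for scheduling, personal or non-drug medical reasons: "The week that durvalumab dose is restarted will be considered Week 1; subsequent treatments/evaluations may then be scheduled accordingly".

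Footnote e also provides for early imaging: "If the patient has CT and/or MRI scans completed early for any reason (i.e. suspicion of disease progression"). The next scan may then be set 8 or 12 weeks from that one.

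Section 14.0 defines PFS by Kaplan-Meier from start of treatment to progression or death. It dates progression for patients treated beyond it, but says nothing on late or missed scans, censoring or interval censoring.

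**The concern.** PFS runs in calendar time, and radiographic progression is known only when a scan is done. If the scan waits for dosing to resume, the recorded date depends on how the drug was tolerated as well as on the disease. The week-based and cycle-based intervals agree only while dosing is on time (2 cycles × 4 weeks = 8 weeks; 3 × 4 = 12). After a hold they diverge, and the text lets the physician follow the cycles.

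At stake is the interpretation of a secondary estimate. With 11 patients, one patient carried past a landmark by a moved scan shifts the estimate by 1/11 = 9.1 points if nobody has been censored.

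**Working it through.** **The plan's own design figure.** The only design calculation is the DLT rule in Section 14.0: stop if DLTs exceed 1 of 3, 2 of 6 or 2 of 11. Exact binomial recursion over stages of 3, 3 and 5 patients gives:

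- DLT rate 0.10: 0.0280 + 0.0075 + 0.0657 = 0.1012 (stated 0.101184466).
- DLT rate 0.35: 0.2817 + 0.1368 + 0.3890 = 0.8075 (stated 0.80748277).

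Both reproduce, and scan timing does not touch them. No calculation is given for PFS.

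**Mechanism in one patient.** Progression occurs at week 20 and the week-24 scan is moved 4 weeks. Progression is dated week 28 instead of week 24, so at a 26-week landmark the patient counts as progression-free. The patient is still an event, only a later one.

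**How long a slip the documents imply.** No scan-delay limit is stated. Appendix 1 gives two rough guides:

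- For many held immune-mediated events, dosing resumes after a steroid taper, and tapers run at least 28 days. Part of a taper can overlap the normal 4-week dosing gap, so 28 days is not automatically a 4-week slip.
- The 12-week limit on reducing steroids runs from the last dose. The next dose is due at week 4, so it implies about 12 − 4 = 8 weeks past the due date. It is a discontinuation criterion, not a scan window.

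**Illustrative simulation.** Assumptions:

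- Exponential progression times, anchored to the 36% 12-month PFS that Section 3.0 quotes for another drug: median = 52.18 × ln 2 / −ln 0.36 = 35.4 weeks.
- Scans at weeks 8, 16 and 24, then every 12 weeks.
- One hold of 2, 4, 8 or 12 weeks, starting uniformly between weeks 4 and 24, in 10%, 20% or 50% of patients still progression-free at that time. All later scans move by the hold.

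Without holds, PFS at 24 weeks is 0.626. Its standard error with 11 patients is √(0.626 × 0.374 / 11) = 0.146.

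| Hold (weeks) | Delay if progression falls between hold onset and the planned scan | Mean change, all held patients (weeks) | Rise in 24-week PFS, 10% / 20% / 50% held (points) |
|---|---|---|---|
| 2 | 2 | −0.05 | 0.7 / 1.3 / 3.3 |
| 4 | 4 | −0.05 | 0.5 / 1.0 / 2.5 |
| 8 | 8 | +0.25 | 0.2 / 0.4 / 1.0 |
| 12 | 12 | +0.85 | 1.0 / 1.9 / 4.8 |

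Reading the table:

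- About 7% of held patients progress between hold onset and the planned scan. They bear the full delay.
- For everyone else the whole later grid has moved, so detection can fall earlier or later. The two largely cancel for short holds.
- Week 24 is itself a scan date, which makes this landmark sensitive to a shift. The 8-week row is low because a week-16 scan moved 8 weeks lands on week 24, not past it.
- The simulated median, 36 weeks without holds, moves up by 0 to 8 weeks here. With a true median of 26 weeks, a 4-week hold and half of patients held, it falls from 36 to 28.

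**Sensitivity.** The table leaves out patients whose disease had already progressed, unseen, when the hold began. Including them, with true medians of 26, 39 and 52 weeks and 20% or 50% held, the rise at 24 weeks runs from 0.6 points (52 weeks, 8-week hold, 20%: 0.728 to 0.734) to 8.5 points (26 weeks, 12-week hold, 50%: 0.527 to 0.612). Repeated holds were not modelled and could add to this.

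**The case against.** The strongest reply is that the permission may seldom matter. Rescheduling is discretionary, the default is in weeks, and early scans are allowed on suspicion of progression, which works the other way. Many toxicities lead to a short hold, no hold or permanent discontinuation: Section 11.1 does not hold Cycles 2 and 3 for cytopenias, and Appendix 1 does not interrupt dosing for isolated hypothyroidism. PFS is a secondary, single-arm estimate in 11 patients with no comparator, test or threshold. All of this stands, and it limits the size of the point. It does not remove it: asymptomatic progression still waits for the scheduled scan, and Section 14.0 has nothing to offset a late one.

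Some stronger readings are tempting, and the documents do not support them:

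- **That dose holds lengthen PFS.** The text permits a shift and does not require it, and the computed effect is not uniformly upward.
- **That footnote a ties scans to toxicity.** It covers only holds for other reasons. The toxicity clauses are the NOTE and Section 11.1.
- **That scans slip 4 to 12 weeks.** Neither Appendix 1 figure is a scan delay, and the 12 weeks count from the last dose.
- **That responses will be missed.** Best response is taken over the whole period to progression, and time to response is not an objective.

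**Conclusion.** The point holds as a permission that should be closed, not as a demonstrated bias. Scan timing can follow toxicity without limit, and a progression in a stretched interval is dated late by up to the shift. The likely effect is upward at an early landmark: about 0.2 to 4.8 points at 24 weeks in the main illustration and up to 8.5 in the widest scenario, all below the standard error of about 14.6. Hold frequency, hold length and the PFS distribution are assumptions, because the documents give none for this trial. No stated figure or stopping rule changes. The change is worth making because it is cheap and removes an avoidable dependence of the endpoint on tolerability.

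**What to change.** In Section 10.1 (footnotes a and e and the NOTE) and in the restart bullet of Section 11.1, state that tumour imaging stays on the protocol's existing calendar from the first durvalumab dose: every 8 weeks to 6 months, then every 12 weeks, each plus or minus 1 week, whatever the dose delays. Only dosing and dosing-linked tests move. Unscheduled scans for suspected progression remain allowed; say whether the next scan then returns to the calendar or follows footnote e's existing 8- or 12-week re-anchoring. A sentence in Section 14.0 on how late or missed scans are handled for PFS would complete the change.

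The cost is small but not nil. Some scans will fall outside dosing visits, and patients with long holds may have an extra scan. A scan due before a delayed RAI dose would have to be done without iodinated contrast, as at baseline, under the restriction already in Section 10.1.

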4.3 Intervention

Enrolled patients will be treated with durvalumab 1500 mg IV approximately every 4 weeks. In Cycle 1/Week 3, Thyrogen 0.9 mg IM will be administered on two consecutive calendar days followed by 100 mCi (+/- 10 mCi) of RAI the next calendar day. Durvalumab will be continued approximately every 4 weeks. Only adverse events occurring within 6 weeks of the first durvalumab dose will be counted as dose limiting toxicities (DLTs). Tumor assessments according to RECIST v1.1 criteria will be conducted with serial radiologic imaging at baseline and approximately every 2 cycles of durvalumab therapy (or every 8 weeks +/- 1 week). After 6 months of treatment, imaging will be obtained every 3 cycles (or every 12 weeks (+/- 1 week)). Patients will remain on durvalumab treatment until there is confirmed progression of disease, unacceptable toxicity, withdrawal of consent, or if the study physician feels removal from the study is in the patient's best interest. One exception to these discontinuation rules: given the potential for delayed responses following short periods of disease progression with immunotherapy, subjects may continue to receive therapy beyond radiographic progression if the investigator concludes that the subject is tolerating study drug and continued therapy may provide clinical benefit. Adverse events will be monitored from the time informed consent is signed until 90 days after the last dose of drug. It is mandatory that patients agree to undergo two research biopsies, which will be analyzed to evaluate how this experimental approach changes the genomic/transcriptomic landscape of the tumor and the tumor immune infiltrate (exemption from the second biopsy may be considered if after performance of the first biopsy it is felt that a subsequent biopsy is not reasonably safe for the patient). Archival tumor tissue and serial peripheral blood collections will also be analyzed for potential biologic correlates of immune activation and efficacy derived from the combination therapy.

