Rationale: We hypothesize that disruption of the PD-1/PD-L1 axis with durvalumab in combination with rhTSH-prepared RAI therapy will alter peripheral blood immune populations. Additionally, T cell receptor repertoire may be analyzed.

Approach: (These studies will be conducted in collaboration with the MSK immune monitoring core facility.) At the time points indicated in **Section 10**, peripheral blood samples will be collected: 4 CPT tubes (BD, 8-ml capacity, total blood volume collected ~32 ml for PBMC purification for flow cytometric analysis) and 1 PAXgene tube (BD order #762165 or equivalent) (for purification of RNA/DNA for TCR analysis). Changes to these methods may be adapted depending upon the most recent, generally accepted protocols. Flow cytometry will be used to evaluate changes in T cell subsets at different time points. Alternative approaches to this analysis may be pursued depending upon the availability of new technologies, platforms, or approaches. Specifically, assays investigating the immunogenicity of tumoral antigens in *ex vivo* assays utilizing these collected PBMCs may be of value and will be performed to identify potential neoantigens or self antigens that are critical for mediating therapeutic efficacy.

Exploratory Objective #2: To investigate changes in cell free DNA (cfDNA) that occur with durvalumab and rhTSH-prepared RAI.

Rationale: We hypothesize that rhTSH-prepared RAI therapy will enhance expression and release of thyroid-specific antigens/neoantigens critical for augmenting immunotherapeutic responses to PD-L1 targeting with durvalumab. Here, we propose using tumor cfDNA as a surrogate marker of tumor lysis and antigen release.

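### Footnote p lets the Cycle 2 cfDNA draw be waived as redundant with draws that all precede RAI, so a patient's only scheduled early post-RAI cfDNA sample may be lost

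*Combined protocol and SAP*

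**What the plan says.** Exploratory Objective #2 for peripheral blood (section 9.5) rests on the hypothesis that rhTSH-prepared RAI increases the release of thyroid antigens. For this purpose "we propose using tumor cfDNA as a surrogate marker of tumor lysis and antigen release". Section 14.0 plans a graphical analysis of how the cfDNA measures change with therapy.

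The sampling times are in the footnotes to the section 10.1 calendar.

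- Footnote o, first draw: "These blood samples (peripheral T cells and cfDNA) will be collected Cycle 1/Week 1 (prior to durvalumab".
- Footnote o, two further cfDNA draws in Cycle 1, Week 3 or 4: "on the day of first Thyrogen injection (but prior to Thyrogen injection) and on the day of RAI administration (but prior to RAI ingestion".
- Footnote p: later T-cell and cfDNA collection "will be conducted on Week 1 of Cycles 2, 3, and 4", preferably before that day's durvalumab, and again at Off Study.
- Footnote p, waiver: "Cycle 2 cfDNA collection does not have to be performed if the Principle Investigator decides that it is redundant". The ground given is that it may be "redundant given the cfDNA collections performed for" footnote o.
- Footnote u: from Cycle 2 on, research collections may be made up to 3 days before treatment.

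**The concern.** A sample is redundant if another sample already carries its information. The waiver points to the footnote o draws for this, but the last of them is taken "on the day of RAI administration (but prior to RAI ingestion". On the planned schedule the Cycle 2 Week 1 sample is therefore the first to follow RAI, and a set of wholly pre-RAI samples cannot replace it.

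At stake is the comparison closest to the stated hypothesis: cfDNA just before RAI against cfDNA soon after it, with RAI the main new exposure in between. Without Cycle 2, the plotted line runs from a pre-RAI point straight to Cycle 3, and by then the patient has also had a second durvalumab dose. The waiver has no criterion for redundancy and only 11 patients are planned, so case-by-case waivers could leave few early values, and an uneven set of them. A sample not drawn cannot be recovered.

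**Working it through.** The plan gives no figure to reproduce here. The check is a day count of the cfDNA schedule.

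**Inputs**

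- Day 1 is the first durvalumab dose. Cycles last about 4 weeks (section 4.3), so Cycle 2 Week 1 starts on Day 1 + 28 = 29 and Cycle 3 Week 1 on Day 1 + 56 = 57.
- Section 4.3: "In Cycle 1/Week 3, Thyrogen 0.9 mg IM will be administered on two consecutive calendar days", with RAI on the following day. Week 3 is Days 15 to 21. The earliest sequence is Thyrogen on Days 15 and 16 with RAI on Day 17. The latest within Week 3 is Thyrogen on Days 19 and 20 with RAI on Day 21.
- Early window for draws from Cycle 2 on: 3 days (footnote u).
- Latest RAI: before the second durvalumab dose (footnote i), so Day 28 at the end of Week 4.

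**Step 1. Position of each Cycle 1 cfDNA draw relative to RAI**

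1. Cycle 1 Week 1, before durvalumab: before RAI.
2. First Thyrogen day, before injection: before RAI.
3. RAI day, before ingestion: before RAI.

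All three precede RAI.

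**Step 2. Days from RAI to the first scheduled post-RAI cfDNA draw** (gap = draw day − RAI day)

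| | RAI Day 17 | RAI Day 21 |
|---|---|---|
| Cycle 2, Day 29 | 29 − 17 = 12 | 29 − 21 = 8 |
| Cycle 2 drawn 3 days early, Day 26 | 26 − 17 = 9 | 26 − 21 = 5 |
| Cycle 3, Day 57 | 57 − 17 = 40 | 57 − 21 = 36 |
| Cycle 3 drawn 3 days early, Day 54 | 54 − 17 = 37 | 54 − 21 = 33 |

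Keeping Cycle 2 gives a first value at 8 to 12 days (5 to 9 if early). Waiving it gives a first value at 36 to 40 days (33 to 37 if early). Each bound moves by the full 28-day cycle.

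**Step 3. Late RAI, Day 28**

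Cycle 2: 29 − 28 = 1 day after RAI, or 26 − 28 = −2, that is 2 days before RAI, if drawn 3 days early. Cycle 3: 57 − 28 = 29 days after RAI, or 54 − 28 = 26 if early.

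**Step 4. The parallel rule for thyroglobulin**

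Footnote r draws TSH and thyroglobulin at the same two points, before Thyrogen and before RAI ingestion, and then at Week 1 of every cycle with no waiver. For that marker the plan does not treat the pre-RAI draws as making Cycle 2 redundant.

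**The case against.** The strongest reply is that the waiver can have a sensible use. Footnote o allows the Thyrogen and RAI-day draws in Week 4, footnote i and section 11.1 allow RAI to be delayed up to the second durvalumab dose, and footnote u allows an early Cycle 2 draw. Step 3 shows that the Cycle 2 sample may then fall a day after the RAI-day sample, or even before RAI. This stands. A reader might infer that the Cycle 2 draw can never be redundant, but the documents support that only for the planned Week 3 schedule. It follows too that deleting the waiver alone would not guarantee a post-RAI sample.

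A reader might also infer that without Cycle 2 an RAI effect on cfDNA could be neither seen nor separated. The documents do not support this. Cycles 3 and 4 and Off Study still give post-RAI cfDNA. Nor would keeping Cycle 2 isolate RAI: the trial has one arm, durvalumab starts about two weeks before RAI, Thyrogen comes immediately before it, and the objective concerns change under the combination. What is lost is the early value and some strength of attribution.

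Nor is all early post-RAI information lost. Cycle 2 thyroglobulin is not waivable, and section 3.0 itself links thyroglobulin rises after RAI to antigen release. The Cycle 2 T-cell samples also remain.

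Finally, a reader might use the stated 8-day half-life of ¹³¹I to measure the loss by the activity remaining at each draw. Physical decay is not cfDNA release. The documents give no cfDNA kinetics or tumour retention figures, so such percentages would not show that one draw is informative and the other is not.

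**Conclusion.** The concern holds in a limited form. On the planned schedule the stated ground for the waiver fails, because every footnote o draw precedes RAI. Using the waiver moves a patient's first scheduled post-RAI cfDNA value from 8 to 12 days after RAI to 36 to 40 days, past a second durvalumab dose. The early change is lost for that patient, and later change is harder to attribute to RAI.

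The reach is narrow. The waiver is discretionary and collection is the default. The objective is exploratory and descriptive, and the safety, BOR and PFS analyses are untouched. An Off Study draw in a patient who leaves before Cycle 3 could come earlier than Day 57, but it is not a planned early sample.

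The day counts assume 28-day cycles without delay and RAI within Week 3. How much cfDNA would change between the two time points cannot be judged from the documents.

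**What to change.** In section 10.1, footnote p, delete the sentence that waives the Cycle 2 cfDNA draw. Alternatively, allow the waiver only for a patient who has another early post-RAI cfDNA sample.

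In either case, state that the Cycle 2 cfDNA sample is to be taken after RAI, so that the 3-day early window in footnote u cannot place it before RAI. Both edits concern sample collection only and leave treatment timing as written.

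The cost is one cfDNA tube and its processing per patient in whom the waiver would have been used. The draw is already scheduled, and T-cell blood is taken at the same time.
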